13.7.4 Record Retention

The Investigator will maintain all study records according to ICH-GCP and applicable regulatory requirement(s). Records will be retained for at least 2 years following marketing application approval or 2 years after formal discontinuation of the clinical development of the investigational product or according to applicable regulatory requirement(s). If the Investigator withdraws from the responsibility of keeping the study records, custody must be transferred to a person willing to accept the responsibility. The Sponsor must be notified in writing if a custodial change occurs.

The Sponsor and Transmural Systems, LLC, have full rights over any invention, discovery, or innovation, patentable or not, that may occur in performing the study.

13.8 Publication and Presentation of Study Findings and Use of Information

It is anticipated that the results of this study will be presented at scientific meetings and/or published in a peer reviewed scientific or medical journal. A Publications Committee comprised of Investigators participating in the study and the Sponsor, as appropriate, will be formed to oversee the publication and presentation of the study results, which will reflect the experience of all participating clinical sites. No publication or disclosure of study results will be permitted except under the terms and conditions of a separate written agreement between Sponsor and the investigator and/or the investigator's institution.

14.0 SPONSOR REGULATORY REQUIREMENTS

14.1 Role of Sponsor

As the study sponsor of this clinical study, [name] has the overall responsibility for the conduct of the study, including assurance that the study meets the regulatory requirements of the appropriate regulatory bodies.

14.2 General Duties

The Sponsor's general duties consist of submitting the appropriate regulatory applications, selecting investigators, obtaining their signed agreement, providing them with the information necessary to conduct the study, ensuring proper clinical site monitoring, and ensuring study subject informed consent is obtained.

14.3 Research Monitoring Plan

An independent research monitor will be designated by the Sponsor. Monitoring will be done by personal visits and will include on-site review of the informed consent documents and case report forms for completeness and clarity, cross-checking with source documents, and clarification of administrative matters will be performed. The review of medical records will be performed in a manner to ensure that subject confidentiality is maintained. The site monitor will ensure that the investigation is conducted according to protocol design and regulatory requirements by frequent communications (letter, e-mail, telephone, and fax).

Data from all treated subjects will be monitored (100% subject monitoring).

14.4 Site Selection and Training

The sponsor or its designee (national co-principal investigator) will ensure appropriate training in the technique of caval-aortic access and operation of the TCD system prior to treatment with the TCD at any participating institution.

14.4.1 Site selection:

Site selection will be based on

- Physician expression of interest and need to apply this treatment approach to patients at the site.
- Physician prior experience with at least 10 successful trans caval access and closure procedures, to assure operator competence
- Site prior participation in IDE protocols evaluating a treatment of structural heart disease
 - Site ability to obtain CT examinations that are satisfactory for consideration of trans caval access.
 - Site investigators willing and able to comply with the requirements of this protocol.

14.4.2 Site training:

Site training will consist of

- Principal investigator and/or sponsor didactic training about the technique, preclinical, and clinical experience to date.
- Proper use of the TCD System and protocol requirements.
- Site Initiation Visits (SIV) will be conducted by the designated monitoring contractor and will be attended by research coordinators, research assistants and other staff participating in this research study. The SIV will typically be conducted prior to enrollment of the first subject.

REFERENCES

15.0 Appendix A: Risk Analysis

Event	Narrative	Probability	Severity	Risk (Probability x Severity)	Available Evidence to Consider Risk	Conclusion and risk mitigation strategy
Death	Death is an expected complication of complex and high risk structural heart interventional procedures, especially in those with no good conventional options.	1	5	5	All testing performed to date in both animal and bench studies has demonstrated that the device is robust and will perform as expected. The TCD was specifically designed to overcome challenges associated with off-label use of commercially-available devices.	The risk, while appreciable, is graded as tolerable in light of the potential benefit. Risk will further be mitigated with informed consent.
Hemorrhage requiring blood transfusion	Hemorrhage is expected after trans caval access and closure. Bleeding attributed to trans caval access is expected to be retroperitoneal (see below).	1	4	4	Animal testing with the TCD demonstrated immediate hemostasis. The TCD was specifically designed to overcome challenges associated with off-label use of commercially-available devices.	This risk is graded as negligible, and justified in light of the potential benefit. Risk will be further mitigated by monitoring of subjects for signs and symptoms of blood loss to allow for early treatment. In addition, the clinical protocol will instruct physicians to deploy a covered stent if required to control bleeding.
Hemorrhagic shock requiring intervention	Persistent bleeding, presumed retroperitoneal, may require additional management including crystalloid, vasopressor, blood transfusion, and mechanical intervention.	1	5	5	Animal testing with the TCD demonstrated immediate hemostasis. The TCD was specifically designed to overcome challenges associated with off-label use of commercially-available devices.	The risk, while tolerable, is considered justified in light of the potential benefit. Risk will be further mitigated by monitoring of subjects for signs and symptoms of blood loss to allow for early treatment. In addition, the clinical protocol will instruct physicians to deploy a covered stent if required to control bleeding.
Persistent aorto-caval fistula requiring intervention	Residual aorto-caval fistula is expected to be universal	1	3	3	Animal testing with the TCD demonstrated immediate hemostasis. The TCD was specifically designed to overcome challenges associated with off-label use of commercially-available devices. Based on clinical features, this aorto-caval shunt is hemodynamically insignificant, especially compared with intentional arteriovenous shunts such as those implanted to facilitate hemodialysis.	This risk is graded as negligible, and justified in light of the potential benefit. Risk will be further mitigated by having the protocol include CT examinations at each follow up through 1 year to monitor the presence of A/V Fistula.

KEY LEVEL	1	2	3	4	5
Probability	Rare	Uncommon	Common	Normal	
Severity	Easy to correct, no anticipated harm to patient	Difficult to correct, no anticipated harm to patient	Potentially harmful to patient	Likely harmful, even with immediate correction	Life threatening
Risk Score	1-4	5-9	10-20	>20	
Risk Interpretation	Negligible	Tolerable	Tolerable but undesirable	Intolerable	

Event	Narrative	Probability	Severity	Risk (Probability x Severity)	Available Evidence to Consider Risk	Conclusion and risk mitigation strategy
Retroperitoneal hemorrhage	Retroperitoneal bleeding is expected in all patients undergoing trans caval access for TAVR. The expected mechanism is that aortic hemorrhage pressurizes the retroperitoneal space causing decompression of the hemorrhage into the hole in the inferior vena cava.	1	3	3	Animal testing with the TCD demonstrated immediate hemostasis. The TCD was specifically designed to overcome challenges associated with off-label use of commercially-available devices.	The risk is rated as negligible. It is considered justified in light of the potential benefit. Risk will further be mitigated with informed consent.
Aortic or other vascular injury such as aortic dissection, pseudoaneurysm or perforation	Heavily diseased aortas may be injured during caval-aortic crossing or during closure device deployment	2	4	8	The TCD Implant and delivery system are designed to overcome challenges associated with off-label use of commercially-available devices. Iatrogenic aortic pseudoaneurysm is part of the spectrum of retroperitoneal hemorrhage, and represents a volume of blood in continuity with the aorta that is partly or completely surrounded by fresh or organized thrombus. We expect the pseudoaneurysm and hematoma, both in physical proximity to the implanted TCD, to resolve in follow-up as part of healing.	The risk is rated as tolerable. It is considered justified in light of the potential benefit. Risk will be further mitigated by monitoring of subjects for signs and symptoms of blood loss to allow for early treatment. The clinical protocol will instruct physicians to use either balloon aortic tamponade or a covered stent in the case of aortic injury. The protocol will include CT examinations at each follow up through 1 year to monitor vascular injury.
Thrombocytopenia or hemolytic anemia as a consequence of aorto-caval fistula	Mechanical injury to blood cells may result from residual aorto-caval shunt after device closure of the caval-aortic access site	1	3	3	Animal testing with the TCD demonstrated immediate hemostasis. The TCD was specifically designed to overcome challenges associated with off-label use of commercially-available devices.	The risk is rated as negligible. It is considered justified in light of the potential benefit. Risk will be further mitigated by monitoring of subjects for signs and symptoms of blood loss to allow for early treatment. The clinical protocol will instruct physicians to use either balloon aortic tamponade or a covered stent in the case of aortic injury. The protocol will include CT examinations at each follow up through 1 year to monitor vascular injury.

KEY LEVEL	1	2	3	4	5
Probability	Rare	Uncommon	Common	Normal	
Severity	Easy to correct, no anticipated harm to patient	Difficult to correct, no anticipated harm to patient	Potentially harmful to patient	Likely harmful, even with immediate correction	Life threatening
Risk Score	1-4	5-9	10-20	>20	
Risk Interpretation	Negligible	Tolerable	Tolerable but undesirable	Intolerable	

Event	Narrative	Probability	Severity	Risk (Probability x Severity)	Available Evidence to Consider Risk	Conclusion and risk mitigation strategy
Late erosion or migration or unexpected perivascular pathology	There is a theoretical risk of unexpected late complications of caval-aortic access and closure, including device erosion, failure, migration, or late vascular or perivascular remodeling or other pathology.	1	4	4	The adaptive geometry of the Intravascular disk and neck along with compression element and outer PET fabric is designed to conform to aortic pathology and irregular mural rents to achieve hemostasis under a range of anatomies. In addition, outer PET fabric is designed to allow for tissue ingrowth for long-term hemostasis.	This risk is graded as negligible and justified in light of the potential benefit. Risk will be further mitigated by the protocol including CT examinations at each follow up through 1 year to monitor the presence of erosion
Nephrotoxic injury due to additional iodinated radio-contrast during trans caval TAVR and associated follow-up	Iodinated radiocontrast is necessary for X-ray procedures including TAVR. Aortography is performed as part of trans caval access and closure and requires iodinated contrast. This may be offset in part or in whole by iodinated contrast not administered as part of management of large-bore arterial access for conventional TAVR	1	3	3		The risk is rated as negligible. It is considered justified in light of the potential benefit. Risk will further be mitigated with informed consent.
Infection, early or late	Prosthetic implants risk early or late infection	2	4	8	Sterilization and packaging validation results confirm that the product, as packaged, will maintain a sterility assurance level (SAL) of 10^{-6} and that the sterile barrier is maintained through transit. Antimicrobial prophylaxis is a routine component of TAVR performed during the same session as the trans caval access and closure.	This risk is graded as tolerable. It is considered justified in light of the potential benefit. Risk will be further mitigated by the IFU including a precaution for physicians to evaluate the packaging at the time of use and to not use product where the sterile barrier may be compromised. In addition, prophylactic antibiotics will be prescribed per standard TAVR follow up.

KEY LEVEL	1	2	3	4	5
Probability	Rare	Uncommon	Common	Normal	
Severity	Easy to correct, no anticipated harm to patient	Difficult to correct, no anticipated harm to patient	Potentially harmful to patient	Likely harmful, even with immediate correction	Life threatening
Risk Score	1-4	5-9	10-20	>20	
Risk Interpretation	Negligible	Tolerable	Tolerable but undesirable	Intolerable	

Event	Narrative	Probability	Severity	Risk (Probability x Severity)	Available Evidence to Consider Risk	Conclusion and risk mitigation strategy
Aortic lumen reduction/ occlusion	During or after placement of the TCD implant, the aortic lumen could be reduced or occluded due to improper placement of the implant.	1	5	5	The TCD implant is designed to be repositionable and re-deployable to allow the physician to optimally place the device. Animal testing has been performed which demonstrates that the TCD can be repositioned and re-deployed with no safety concerns.	The risk is rated as tolerable. It is considered justified in light of the potential benefit. Risk will be further mitigated by the instructions for use and user training providing users information on how to recognize improper device orientation under imaging and how to correct the orientation. The clinical protocol will instruct physicians to use either balloon aortic tamponade or a covered stent to aid with re-opening of the lumen.
Thromboembolism / Thrombosis	During or after placement of the TCD implant, thrombosis of the implant could occur due to improper placement of the implant.	1	4	4	The TCD implant is designed to be repositionable and re-deployable to allow the physician to optimally place the device. Animal testing has been performed which demonstrates that the TCD can be repositioned and re-deployed with no safety concerns. Animal testing has been performed and no thromboembolism/thrombosis observed grossly or via histopathology.	This risk is graded as negligible, and justified in light of the potential benefit. Risk will be further mitigated by the instructions for use and user training providing users information on how to recognize improper device orientation under imaging and how to correct the orientation.
Venous thrombosis or thromboembolism	Thrombosis may occur related to the femoral vein access site, related to the TCD implant, or causing thromboembolism from either nidus.	2	4	5	Large-bore femoral vein access is a common step in structural heart interventional procedures such as Mitraclip and transcatheter mitral valve implantation. Catheter related femoral thrombosis is treated only if clinically symptomatic and manifest. TCD thrombogenicity is evaluated pre-clinically. TCD is expected to encroach on IVC less than comparator Amplatzer devices implanted in the trans caval position.	The risk is rated as tolerable. It is considered justified in light of the potential benefit. Risk will be further mitigated through CT evaluation of the TCD implant site during follow-up, and by clinical surveillance for adverse events.

KEY LEVEL	1	2	3	4	5
Probability	Rare	Uncommon	Common	Normal	
Severity	Easy to correct, no anticipated harm to patient	Difficult to correct, no anticipated harm to patient	Potentially harmful to patient	Likely harmful, even with immediate correction	Life threatening
Risk Score	1-4	5-9	10-20	>20	
Risk Interpretation	Negligible	Tolerable	Tolerable but undesirable	Intolerable	

Event	Narrative	Probability	Severity	Risk (Probability x Severity)	Available Evidence to Consider Risk	Conclusion and risk mitigation strategy
Adverse biological reaction	The materials of the TCD implant or delivery system have the potential to illicit a biological response due to non-compatibility.	1	4	4	The materials for the delivery system and the implant were selected based upon known previous biocompatibility with blood and tissue. A suite of biocompatibility testing has been performed which demonstrates the delivery system and the implant are non-toxic and not expected to illicit an adverse biological response.	This risk is graded as negligible, and justified in light of the potential benefit. Risk will be further mitigated by monitoring of subjects for signs and symptoms of allergic reactions. Labeling will include a contraindication for patients allergic to nickel.
Thermal injury	The TCD is a permanent implant constructed of metal and therefore may be susceptible to heating in a MRI environment	1	3	3	1.5T and 3.0T testing in a standard MRI demonstrates that the TCD Implant is MR Conditional.	This risk is graded as negligible, and justified in light of the potential benefit. Risk will be further mitigated by the IFU and patient implant card providing the information to support appropriate MRI use.

KEY LEVEL	1	2	3	4	5
Probability	Rare	Uncommon	Common	Normal	
Severity	Easy to correct, no anticipated harm to patient	Difficult to correct, no anticipated harm to patient	Potentially harmful to patient	Likely harmful, even with immediate correction	Life threatening
Risk Score	1-4	5-9	10-20	>20	
Risk Interpretation	Negligible	Tolerable	Tolerable but undesirable	Intolerable

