5.0 STUDY DESIGN

5.1 Schematic of study design

5.2 Overview of study design

This is an early feasibility study of the TCD. It is a prospective, open-label, single-arm, multi-center, investigator-initiated, and independently-adjudicated investigation of the TCD in patients undergoing TAVR who are not eligible for standard transfemoral artery access.

Candidates will be identified by the participating structural heart disease programs. Standard TAVR planning includes contrast-enhanced abdomen and pelvis CT, typically during the same contrast exposure as the cardiac CT. Eligibility will be reviewed and proposed by the local multidisciplinary heart teams. Anatomic eligibility will be confirmed by the core CT analysis laboratory using the clinically indicated CT. Candidates will then undergo central eligibility review by the Study Eligibility Committee. If deemed eligible, candidates will be offered participation in the study.

Once enrolled, subjects will undergo protocol baseline assessment. If eligible, subjects will be admitted to the hospital and undergo trans caval TAVR under this protocol. The trans caval access site will be closed with the TCD. They will undergo follow-up testing including CT scan at 30 days and 12 months.

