5.4 Time and Events Schedule

				12 mo (± 4 wk) FU		
				6 mo (± 3 wk)		
				30 d (± 14 d) FU		
Screening (-30 to 0D)	Baseline	Day 0	Inpatient			
Baseline informed consent		X				
Multidisciplinary heart team eligibility determination		X				
Baseline clinical assessment		X				
Blood tests		X		X	X	X
Vital signs and in-person visit		X		X		X
Abdomen/pelvis CT (contrast-enhanced) analyzed by core lab	X			X		X
Study eligibility committee concordance	X					
Transcaval TAVR with implantation of transcaval closure device (TCD)			X			
Vital status and adverse event assessment				X	X	X

Subjects will receive continuing care from their primary physicians with consultant input as requested from the structural heart disease program.

For subjects who die, necropsy evaluation is requested to examine the abdominal aorta and cava *en bloc* at NIH.

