6.0 ELIGIBILITY ASSESSMENT

6.1 Inclusion Criteria

- Consents to participate in this study and all related clinical follow-up procedures
- Adults age ≥ 21 years
- Undergoing transcatheter aortic valve replacement (TAVR) based on the clinical assessment of the multidisciplinary heart team
- Ineligible for femoral artery access for the selected transcatheter heart valve (THV) according to the THV manufacturer instructions for use.
[Note Corevalve Evolut R: ≥ 5 mm; Evolut PRO 23, 26, 29 mm valves and Evolut R 34 mm: ≥ 5.5 mm; Edwards Sapien 3, 23-26mm: 5.5 mm; Edwards Sapien 3, 29mm: 6.0mm;
Anatomic ineligibility also considers patient-specific pattern of iliofemoral calcium and tortuosity.]
- Eligible for trans caval access based on Core Lab analysis of the baseline abdomen/pelvis CT indicating a calcium-free target window on the abdominal aorta; a target ≥ 15 mm from the lowest main renal artery or aorto-iliac bifurcation; no important interposed structures; a projected intravascular centerline distance from the lower femoral head to the target at least 5cm less than the intended THV introducer sheath; patent celiac or superior mesenteric artery;

- Aorta diameter $\geq 11\text{mm}$ at the target crossing site
- Concordance of the study eligibility committee

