6.2 Exclusion criteria

- High risk features on baseline CT including porcelain aorta (confluent calcification); pedunculated aortic atheroma; or leftward aortic angle $\geq 20^\circ$ with regard to vertical;
- Renal dysfunction limiting follow-up contrast-enhanced CT (estimated glomerular filtration rate, eGFR $< 30 \text{ mL/min}/1.73\text{m}^2$ if not already on renal replacement therapy)
- Pregnancy or intent to become pregnant prior to completion of all protocol follow-up procedures

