6.3 Rationale for selection criteria

The selection criteria allow enrollment of the intended population with little anticipated selection bias. The main selection criteria are ineligibility for standard transfemoral artery access, and anatomic eligibility for trans caval access as published⁹. Patients are excluded if there are high risk features such as high risk of atheroembolism. Preclinical data are limited supporting application of the TCD in aortas smaller than 11mm, and therefore such subjects are excluded.

Contrast-enhanced CT during follow-up risks acute and chronic renal failure in patients with baseline renal dysfunction if they are not already on renal replacement therapy. Therefore candidates are excluded if they are not on renal replacement therapy and have eGFR $< 30 \text{ mL/min}/1.73\text{m}^2$.

No patient will be excluded from participation based on sex, gender, race or ethnicity. There is no biological rationale or evidence for sex-specific risk for complications of trans caval TAVR or TCD closure.

The inclusive selection criteria and geographic extent of enrolling sites are expected to allow recruitment of a diverse economic, ethnic, and racial mix of patients that reflects the incident disease, despite the small sample size. Specifically, the results are expected to be generalizable to Medicare and Medicaid beneficiaries because of age and disease-related disability.

A study eligibility committee led by the NHLBI sponsor is convened to assure each subject meets selection criteria before treatment (see section 13.4), and that at least one member has no actual or perceived financial conflict of interest.

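### Appendix A plans a labelled contraindication for nickel allergy, but none of the eligibility criteria in sections 6.1 and 6.2 mentions nickel or device-material allergy

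*Combined protocol and SAP*

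**What the plan says.** Section 12.0 describes a closure device with a nitinol wire frame, and the thermal injury entry in Appendix A calls it a permanent metal implant. The adverse biological reaction entry in Appendix A lists two further mitigations. One is monitoring subjects for allergic reactions. The other is "Labeling will include a contraindication for patients allergic to nickel".

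Section 6.1 has seven inclusion criteria, the last being "Concordance of the study eligibility committee". Section 6.2 has three exclusion criteria, the last being "Pregnancy or intent to become pregnant prior to completion of all protocol follow-up procedures". Section 6.3 describes the committee's job: "A study eligibility committee led by the NHLBI sponsor is convened to assure each subject meets selection criteria before treatment".

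Section 5.2 sets out the route to treatment. "Eligibility will be reviewed and proposed by the local multidisciplinary heart teams"; the core laboratory then confirms anatomy and the committee reviews the candidate. After enrolment comes a baseline assessment, and then: "If eligible, subjects will be admitted to the hospital and undergo trans caval TAVR under this protocol". The schedule in section 5.4 names the clinical steps only as "Multidisciplinary heart team eligibility determination" and "Baseline clinical assessment".

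Section 10.1 includes hypersensitivity to the TCD or its components among the anticipated device effects.

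**The concern.** The sponsor intends the device to be contraindicated in a defined group of patients, yet the written rules for choosing subjects do not mention that group. A site that applied the listed criteria correctly could put forward such a patient, and a check against those criteria would not flag it.

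Timing makes this more than a drafting matter. Of the two further mitigations in the Appendix A entry, monitoring can work only once the subject has been exposed to the device; the contraindication is the one that works beforehand. If the conflict came to light only after transcaval access, the aortic opening would already exist. One of the contingencies that section 5.3 lists for TCD failure is an Amplatzer device, which section 3.0 also describes as nitinol.

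**Working it through.** No figure in the plan bears on this point, so the check is a count of the criteria and a comparison of sections.

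**Eligibility criteria (sections 6.1 and 6.2)**

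| No. | Subject of the criterion | Mentions nickel or device-material allergy? |
|---|---|---|
| Inclusion 1 | Consent | No |
| Inclusion 2 | Age | No |
| Inclusion 3 | Undergoing TAVR on heart-team assessment | No |
| Inclusion 4 | Not eligible for femoral artery access | No |
| Inclusion 5 | Transcaval anatomy on CT | No |
| Inclusion 6 | Aortic diameter | No |
| Inclusion 7 | Committee concordance (general) | No |
| Exclusion 1 | High-risk CT features | No |
| Exclusion 2 | Renal dysfunction | No |
| Exclusion 3 | Pregnancy | No |

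Total: 7 + 3 = 10. Leaving out the one general item: 10 - 1 = 9 specific criteria. Mentions of nickel or device-material allergy: 0 of 10. The count is by bullet; splitting the compound bullets would raise the total but not the number of mentions.

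**Other sections where a screen might appear.** The selection rationale (6.3), the indications for use (12.1) and the committee section (13.4) do not mention nickel allergy. Reactions to the device or catheter materials appear in section 10.1, but as anticipated effects, not as grounds for selection.

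**General steps that could identify such a candidate**

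| Step | Where | What the text says about allergy |
|---|---|---|
| Heart-team determination | 5.2, 5.4 | Nothing |
| Baseline assessment and the eligibility condition after it | 5.2, 5.4 | Nothing |
| Eligibility committee | 6.1, 6.3, 13.4 | Nothing; 6.3 ties its task to the selection criteria |
| Device training before treatment | 14.4 | Nothing |

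That is 0 of 4. The order also matters: section 5.2 puts committee review before enrolment and the baseline assessment after it, so an allergy first recorded at baseline would come to light after the committee had decided.

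**The sponsor's own weighting (Appendix A).** Risk = probability x severity = 1 x 4 = 4. In the key, probability 1 is rare, severity 4 is one level below life-threatening, and a score of 1 to 4 is negligible. The entry is therefore at the top of the negligible band.

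**Number of subjects.** Section 9.1 plans 15 subjects with attempted closure. The expected number affected would be 15 x prevalence of nickel allergy among candidates. The documents give no prevalence, so no figure can be derived.

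**The case against.** The strongest reply is that nothing is contradicted. Appendix A distinguishes its channels of control: some entries say the protocol will instruct physicians, while others rely on labelling or instructions for use. Nickel allergy was assigned to labelling, and no eligibility criterion was promised. The sheath-size limit in section 12.1 likewise stays in the indications for use and is not repeated in section 6. It is correct that Appendix A promises labelling only. But practice is not uniform: section 6.3 explains that the aortic-diameter limit became an eligibility criterion because preclinical support was limited. A reader cannot infer that device limits are deliberately kept out of section 6.

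A second reply is that the device label, case report form, consent form and training content are not available here, and any of them might stop such a candidate. Silence in a one-line schedule entry is weak evidence that allergy history goes unasked. This stands, and it limits the conclusion to the mismatch in the text. It does not alter what the eligibility criteria say.

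A third is that nobody is eligible on nine criteria, because committee concordance is itself the tenth, and section 13.4 has the committee confirm clinical data and record its considerations. Section 14.4.2 also includes proper use of the TCD in site training. These are real safeguards that could work through judgement. None is written to look for nickel allergy.

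Finally, the risk is small. It is graded negligible, and the same Appendix A entry cites material selection and biocompatibility testing, which also act before exposure. This is a fair argument about weight, and it is accepted as such.

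**Conclusion.** The concern holds as a low-weight consistency point. The sponsor plans a labelled contraindication for nickel allergy in a permanent nitinol implant, and a candidate with that allergy can satisfy all 9 specific eligibility criteria.

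Confidence in the textual mismatch is high. How often it would matter in practice is unknown: it depends on the prevalence of nickel allergy and on documents that are not available here, including the label. No endpoint, stopping rule or analysis is affected. It is still worth correcting, because this is a first-in-human study, the sponsor itself anticipates hypersensitivity to the device, and the correction is cheap.

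**What to change.** Reconcile section 6.2 with the adverse biological reaction entry in Appendix A, so that eligibility review and labelling agree before transcaval access is attempted in any subject. Either the eligibility text reflects the planned contraindication, or the protocol states that the contraindication does not apply in this study and the Appendix A entry is revised to match. The choice is the sponsor's, and this review takes no position on it.

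The first route costs one eligibility line with a corresponding check, and may exclude an occasional candidate. The second costs one edited table entry. Neither changes the sample size or the analysis.
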